## SCHEMA

*\* pre- and on-treatment tumor biopsies are required, if safe and feasible (a post-treatment biopsy at the time of disease progression will be offered)*

**Primary endpoint:** objective response rate (ORR) by RECIST v1.1

**Secondary endpoints:** progression-free survival (PFS), overall survival (OS), changes in *MYB* expression among tumor cells and circulating tumor (ct)DNA

## 1. OBJECTIVES

### 1.1 Study Design

This is an open-label, single arm, phase II study of tretinoin (all trans retinoic acid, ATRA) in patients with advanced, unresectable, or recurrent/metastatic adenoid cystic carcinoma (ACC). All participants will have evidence of disease progression, or lack of benefit from standard therapies. All participants will have measurable disease amenable to disease monitoring. Participants in Cohort 1 will receive tretinoin 45 mg/m^2 orally divided over two daily doses for 14 days of a 28-day cycle until disease progression or unacceptable toxicity. Participants in Cohort 2 will receive tretinoin 45 mg/m^2 orally divided over two daily doses continuously during a 28-day cycle until disease progression or unacceptable toxicity. Our aim is to evaluate the anti-tumor activity of tretinoin by inhibition of MYB expression in advanced ACC patients. Correlative studies are planned to evaluate the effect of tretinoin on *MYB* expression in tumor tissue before and after dosing, and to measure circulating tumor (ct)DNA in serum samples while on therapy.

### 1.2 Primary Objectives

To evaluate the anti-tumor activity of tretinoin by evaluating the best overall response rate using RECIST v1.1 in participants with advanced adenoid cystic carcinoma.

### 1.3 Secondary Objectives

- To estimate progression-free survival (PFS) and overall survival (OS)
- To estimate duration of therapeutic response
- To evaluate the inhibitory effect of tretinoin on *MYB* expression in ACC tumors
- To evaluate ctDNA as a biomarker of disease activity in ACC based on response to therapy
- To develop novel patient-derived tumor xenograft (PDX) models from *MYBL1*-rearranged ACC tumors to understand mechanisms of resistance to tretinoin

[figure not shown]
## 2. BACKGROUND

### 2.1 Study Disease(s)

Adenoid cystic carcinoma (ACC) is a common malignancy arising often in salivary gland tissue, often affecting patients with no identifiable risk factors. Localized disease is generally managed with oncologic resection followed by adjuvant radiotherapy in most cases, given the potential for perineural invasion (PNI) linked with this malignancy [1, 2]. Concurrent adjuvant chemoradiotherapy is sometimes offered to mitigate the risk of locoregional recurrence, but no prospective trials have proved that this strategy is beneficial in terms of disease control rates and survival [3]. Despite initial multimodality therapy in the upfront setting, nearly half of ACC patients develop distant, metastatic spread of disease; but the natural history of such cancers is often reflective of slower growth velocity despite recurrences that involve the lungs, liver and bones [4].

There remain no approved systemic cytotoxic or targeted therapies available for the treatment of salivary gland cancers broadly, and none specifically for ACC. While some agents have demonstrated modest disease activity, there has been no overall or progression-free survival advantage observed with any particular agent(s) – therefore the optimal regimen remains unclear [5]. Cytotoxic chemotherapy combinations using anthracyclines, platinum and fluoropyrimidines, and vinorelbine in some combination may have some benefit in a limited number of ACC patients, but their expected toxicities and lack of durable response make them less than appealing when considering that patients with ACC can have slow growing, metastatic tumor burden but maintain a favorable quality of life over months to years [6, 7]. The **Table below** summarizes response rates among ACC patients treated with various cytotoxic regimens [5]. While combination therapies result in greater response rates, there is no clear survival advantage to such an approach and they come with toxicity. Although immune checkpoint blockade has revolutionized cancer immunotherapy with the success of PD-1 inhibitors in a host of solid tumors, ACC does not generally express the ligand of PD-1 (PD-L1) and appears to maintain minimally immunogenic potential [8]. Early studies investigating PD-1 blockade in all salivary cancer patients have been largely disappointing with response rates < 15% in selected PD-L1+ salivary tumors [9].

More recent approaches to treatment have incorporated molecular and genomic profiling data. While no driver mutation is known, these tumors have a low somatic mutation rate when compared with other histologic subtypes of cancer. Multi-targeted tyrosine kinase inhibitors (TKIs) such as sorafenib, and oral therapies targeting c-kit (imatinib, dasatinib) have been investigated with limited objective response rates (< 15%) [10-12]. Next-generation sequencing data has suggested frequent alterations in a diverse array of signaling pathways including: epigenetic modifiers, DNA damage and repair signals, *NOTCH* pathway, and *FGF-IGF-PI3K* signaling [13]; and clinical trials are ongoing to evaluate the anti-tumor effects of drugs aimed at modifying these aberrant signaling cascades in ACC.

Chemotherapy	# of responses/total patients	Response rate (%)
Cisplatin	2/32	6
Vinorelbine	2/13	15
Mitoxantrone	5/50	10
Epirubicin	2/20	10
Paclitaxel	0/14	0
Cyclophosphamide + doxorubicin + cisplatin	12/43	28
Cisplatin + anthracycline + 5-FU	6/19	32
Cisplatin + vinorelbine	4/9	44
Carboplatin + paclitaxel	2/10	20
Cisplatin + gemcitabine	2/10	20

One molecular aberration that has been identified in sequenced ACC tumors is the *MYB-NFIB* fusion oncogene generated by a t(6;9) translocation which occurs in up to 70-90% of ACC tumors (**Figure upper right**) [13, 14]. More than just generating *MYB* gene fusion transcripts, studies have shown that *MYB* mRNA is overexpressed among some of these tumors – pointing to the importance of this molecular event in ACC. Despite the identification of *MYB* has an important target in ACC, no *MYB* inhibitors have been identified. [name] and colleagues recently ran a

chemical screen for bioactive molecules against a *MYB* reporter assay in an animal model and identified retinoic acid compounds, including tretinoin as a potential *MYB*-inhibitory agent [15]. Therefore, evaluating the anti-tumor activity of tretinoin in advanced ACC patients seems a logical next-step in understanding the therapeutic potential of retinoic acids in this disease. Given historical objective response rates of single-agent chemotherapy and multi-targeted TKIs approaching 10% or less, we aim to evaluate if tretinoin may produce similar or superior response rates in advanced ACC.

## 2.2 IND Agent: Tretinoin (All-trans retinoic acid, ATRA)

### 2.2.1 Tretinoin

#### 2.2.1.1 Mechanism of action

The retinoids are a pharmacologic class consisting of vitamin A (retinol) and related derivatives. Retinol and its metabolites play a critical role in cell growth, vision, reproduction, and epithelial cell differentiation, along with immune function [16]. Tretinoin is a natural retinol metabolite formed from intestinal oxidation of beta-carotene and from tissue anabolism of retinaldehyde. Normal serum concentrations are 10-20 nanomolar (nM) [17] which is 10 to 100-fold less than the retinoid concentrations achieved with pharmacologic therapy [18].

The *MYB* family of transcription factors is implicated in cell growth and proliferation, having been linked to leukemic transformation as *MYB* blocks differentiation of hematopoietic cells in preclinical models [19, 20]. Moreover, targeting of *MYB* with antisense oligonucleotides blocks hematopoiesis and therefore myeloid leukemic cell proliferation [21]. Expression of *MYB* declines in retinoic acid-treated myeloid leukemic cells, which suggests that the retinoic acid receptor (RAR) partakes in the downregulation of *MYB* expression [22]. A physical interaction appears to exist between *MYBi* and the RAR, while little is actually known about the details of these mechanistic processes [23].

#### 2.2.1.2 Preclinical safety

The HL-60 cell line is derived from an individual with acute promyelocytic leukemia (APML) which proliferates *in vivo* with a dominance of promyelocytes. Early preclinical experiments with tretinoin showed that differentiation (as measured morphologically) was induced at drug concentrations as low as 1 nM, a value 1/500th to 1/160,000th the concentration of butyrate and dimethyl sulfoxide that similarly promote increased differentiation among promyelocytes [24].

#### 2.2.1.3 Clinical pharmacology and safety

Plasma levels of tretinoin after oral administration can be somewhat variable. Following a 45 mg/m^2 oral dose of tretinoin, peak plasma concentrations on the first day of dosing range from 0.1 to 8 μM, with median concentrations of approximately 1 μM. Plasma and urinary concentrations of the parent compound of tretinoin and metabolites was quantified in 13 patients by reverse-phase high-performance liquid chromatography, showing that mean peak plasma levels of tretinoin were around 347 ng/mL and were reached within 1-2 hours after ingestion. Elimination of tretinoin appears rapid with a terminal half-life of around 45 minutes with a monoexponential decay [25, 26]. The only

metabolite detected in plasma or urine was 4-oxo-all-trans RA which accounted for less than 10% of the circulating drug levels in plasma, and less than 1% in urine. No drug was detected in cerebrospinal fluid. Continued oral administration of tretinoin was associated with a decrease in the plasma peak levels and area under the concentration-time curve when measured 2-6 weeks on treatment. It should be noted that this decrease is associated with an increase in urinary excretion of the 4-oxo-all-trans RA metabolite which suggests some degree of drug catabolism over time [18]. While these limitations have resulted in intravenous (IV) formulations being developed, plasma concentrations appear similar to oral dosing in nonhuman primate models, with a similar decline in plasma area under the curve (AUC) as soon as three days into dosing [27].

Further studies have investigated intermittent dosing schedules (7 days on/7 days off) and have shown that plasma AUC declines significantly during the first week of administration from a mean AUC of 145  $\mu\text{M}\cdot\text{min}$  on day 1 to a mean of 4  $\mu\text{M}\cdot\text{min}$  on day 7. But, plasma tretinoin concentrations at the start of weeks 3 and 11 of this every-other-week schedule were equivalent to those achieved on day 1 of therapy. Thus, intermittent schedules of administration appear to circumvent the low plasma drug exposure that results from sustained upregulation of catabolism that has been observed with daily dosing schedules [28]. This was the rationale for on/off dosing in Cohort 1.

Since tretinoin appears to partially induce its own metabolism, research has focused on inhibitors of tretinoin to combat resistance in APLM [29]. Tretinoin is subject to hydroxylation by the cytochrome P450 26A1 isoform (CYP26A1), thus studies have attempted to inhibit tretinoin metabolism by administering ketoconazole or liarozole – despite their known toxicity profiles. This strategy has even been labeled retinoic acid metabolism blocking agents (RAMBAs) to enhance the clinical efficacy of tretinoin.

The toxicity profile of tretinoin is usually minor and includes headache, low grade temperatures, generalized weakness and some component of fatigue – seldom are any of these effects permanent or irreversible. Common toxicity reported in > 10% of treated patients with tretinoin include: peripheral edema (52%), headache (86%), malaise (66%), skin rash or dry red skin (54%), dry mucus membranes or nasal stuffiness, chapped lips (50%), elevated liver function tests, enzymes or bilirubin (50%), ostealgia (77%), or low-grade temperatures (78%) [30, 31]. While uncommon, other significant adverse events have been reported: venous thrombosis and myocardial infarction have been reported in patients without cardiac risk factors, and the risk of thrombosis (arterial or venous) appears increased within the first month of therapy. CNS effects such as dizziness, headaches or malaise have been reported. Hypertriglyceridemia or hypercholesterolemia has been reported in a number of patients which appears reversible following discontinuation of therapy. Pseudotumor cerebri (benign intracranial hypertension) has been reported, especially in children. Tretinoin has a high-risk of teratogenicity [32, 33]. Importantly, the two serious side effects of differentiation syndrome and hyperleukocytosis are **only** observed when tretinoin is used to treat APLM.

#### 2.2.1.4 Clinical efficacy

As early as 1996, data was published that established the clinical safety and efficacy of tretinoin in the management of patients with de novo APLM. One early protocol utilized a dose of 15-20  $\text{mg}/\text{m}^2/\text{day}$  in 27 patients with newly diagnosed disease and demonstrated a 92% clinical complete

response (CR) rate among 26 evaluable patients within 13-67 days of tretinoin therapy [34]. No cases of retinoic acid syndrome (RAS) or hemorrhagic disseminated intravascular coagulation (DIC) were observed. These data supported the use of low-dose tretinoin in leukemic patients. A further protocol evaluated the efficacy and safety of tretinoin along to induce remission among 53 children with APML. The overall CR rate was 81% with an estimated 5-year disease-free survival (DFS) of 41% and overall survival (OS) of 69% [35]. Moreover, 10-year follow-up of the cohort revealed that OS rates were stable.

Tretinoin has also been successfully and safely combined with chemotherapy. The North American Intergroup regimen is comprised of tretinoin plus daunorubicin (an anthracycline) plus cytarabine (AraC) using the standard 45 mg/m^2/day divided dosing until CR; demonstrating overall CR rates of 90%, and when followed by arsenic trioxide (ATO) consolidation, event-free survival was 80% and OS 86% at 3-years [36]. In the AIDA protocol, tretinoin is combined with idarubicin alone (another anthracycline) but without AraC. Remission rates approached 95% and again utilized the same tretinoin dosing at 45 mg/m^2/day followed by both consolidation and maintenance therapy with an event-free survival at 12 years of 69% [37]. In hopes of avoiding chemotherapy altogether, the Lo-Coco regimen combined tretinoin with ATO at similar dosing and despite shorter follow-up yielded a > 85% remission rate, therefore supporting its role in managing low-to-intermediate risk APML patients, or in those who should not receive anthracycline-based therapy [38]. Combining tretinoin, ATO and gemtuzumab ozogamicin appears to yield response rates of 92%, with an estimated 3-year survival of 85% -- although toxicity has been a concern with an 8% rate of disease-related complications leading to death with this particular regimen [39]. In terms of long-term dosing, as part of consolidation and maintenance therapy for APML, tretinoin is dosed at 45 mg/m^2/day orally days 1-7 during consolidation, and 45 mg/m^2 orally daily on an intermittent schedule of 15 days on every 3-months or 7 days every 2 weeks for up to 1-year during the maintenance phase [36].

[figure not shown]

compounds, (C) and the final average tumor growth inhibition across three human tumors with RA treatments. The authors were able to show that continuous dosing was required to maintain response, as discontinuation of tretinoin resulted in tumor resurgence in ACC x6, x9.

Tretinoin was mechanistically found to interrupt the autoregulatory enhancer loop that occurs with fusion genes involving *MYB*, thus dramatically lowering the level of the oncogenic fusion protein [Figure, below]: (A) Chromosomal rearrangements that maintain *MYB* over-expression in ACC are shown with *MYB*, RAR-binding, and H3K27ac profiles shown at the *MYB* locus or downstream of *NFIB* exon 9 in ACC x9 tumors that have *MYB-NFIB* translocations. Previously described translocated *MYB*-bound enhancers are labeled En1 and En2. We observed a strong decrease in *MYB* binding due to tretinoin treatment at two translocated enhancers in the downstream region of *NFIB* that is fused to the *MYB* locus in one of the ACC primagraft models (ACC x9). In addition, there was a concomitant decrease in H3K27ac (marking active enhancers) at these enhancer sites. Upon tretinoin treatment, we found that retinoic acid receptor alpha (*RARα*) binds physically at the 5' region of the *MYB* gene and at the translocated enhancer, and we confirmed that these sites have *RARα* binding motifs as determined by the JASPAR database [45]. Tretinoin stimulated increased *RAR* expression due to positive autoregulation by the bound receptor; these elevated *RAR* levels cause suppression of *MYB* gene expression or displaces *MYB* binding. Therefore, *RARα* expression appears to serve as a marker of response to tretinoin.

These findings taken together, plus the existing FDA approval of tretinoin for APL, and its known tempered toxicity profile, together provide a strong rationale for testing whether tretinoin elicits a clinical benefit in ACC patients via *MYB* inhibition. Our goal for this project is to translate the basic and preclinical findings for the use of tretinoin in ACC to the clinic.

## 2.4 Correlative Studies Background

As part of this clinical study using tretinoin in advanced ACC, we will examine proof of the mechanism of tretinoin in ACC patient-derived tumor specimens, and further aim to identify candidate biomarkers and mechanisms of resistance to this novel therapy. We expect that interrogation of paired tumor specimens and correlation with clinical response will elucidate the inhibitory effects of tretinoin on *MYB* in ACC, therefore revealing possible mechanisms of activity and resistance. We will uncover novel biomarkers of response or resistance to *MYB*-directed therapy in ACC patients, by interrogating a repository of tumor tissue and peripheral blood obtained from

tretinoin-treated ACC patients. Establishing the first *MYBL1*-rearranged and tretinoin-resistant PDX models will yield insights into possible mechanisms of tretinoin activity and resistance.

We intend to interrogate circulating tumor (ct)DNA as a biomarker of ACC activity and of response to tretinoin therapy. Sensitive techniques have been developed recently for analyzing such “liquid biopsies”, to monitor ctDNA and circulating tumor cells (CTCs) as surrogate markers for tumor burden [46]. These techniques, in combination with imaging studies, offer a valuable approach for assessing tumor response. Tracking tumor-associated genetic aberrations in the blood can also be employed to assess residual disease, or to detect the emergence of cancer cells that are resistant to the therapy; and monitoring genetic alterations found in the blood plasma can be utilized to detect local recurrence or distant metastasis, as early as 5-10 months before they are detectable by conventional imaging [47, 48]. In the proposed study we aim to establish the utility of ctDNA as a biomarker in ACC. This is the first application of ctDNA as a marker of response to *MYB*-directed therapy in ACC, and will pave the way for future studies to validate ctDNA as a predictor of disease burden and clinical outcomes.

### 3. PARTICIPANT SELECTION

#### 3.1 Eligibility Criteria

Participants must meet the following criteria on screening examination to be eligible to participate in the study:

1. Participants must have histologically confirmed adenoid cystic carcinoma with evidence of recurrent, metastatic or advanced, unresectable disease that is not amenable to curative surgery with or without radiotherapy.
2. Participants must have at least one RECIST v1.1 measurable non-CNS based lesion, as defined as at least one lesion that can be accurately measured in at least one dimension (longest diameter to be recorded for non-nodal lesions and short axis for nodal lesions)  $\geq 1$  cm with CT scans or MR imaging.
3. Participants must be willing to undergo fresh tissue core needle biopsy prior to study registration and repeat tumor biopsy while on study for correlatives. Willingness to provide blood samples for research throughout the study is also required.
4. Prior systemic therapy: At least 2 weeks must have elapsed since the end of prior chemotherapy, biological agents (4 weeks for anti-cancer monoclonal antibody containing regimens) or any investigational drug product, with adequate recovery of treatment-related toxicity to NCI CTCAE Version 5.0 grade  $\leq 1$  (or tolerable grade 2) or back to baseline (except for alopecia or neuropathy). Any number of prior therapies for recurrent/metastatic ACC are permitted.
5. Be  $\geq 18$  years of age on day of signing informed consent.
6. Have a performance status of 0 or 1 on the ECOG Performance Scale (see *Appendix A*).
7. Participants must have documentation of a new or progressive lesion on a radiologic imaging study performed within 12 months prior to study registration (progression of disease over any

interval is allowed) and/or new or worsening disease-related symptoms within 12 months prior to study registration. This assessment is performed by the treating investigator. Evidence of progression by RECIST v1.1 criteria is not required.

8. Participants must have normal organ and marrow function as defined below (within 14 days prior to study registration):
  - leukocytes  $\geq 3,000/\text{mcL}$
  - absolute neutrophil count  $\geq 1,500/\text{mcL}$
  - hemoglobin  $\geq 9 \text{ g/dL}$  without transfusion within 7 days of treatment
  - platelets  $\geq 100,000/\text{mcL}$
  - total bilirubin  $\leq 2\text{x}$  upper limit of normal (ULN)
  - AST(SGOT)/ALT(SGPT)  $\leq 2.5\text{x}$  institutional ULN or  $\leq 5\text{x}$  ULN for those with liver metastases
  - serum creatinine  $\leq 1.5\text{x}$  ULN

OR

  - creatinine clearance  $\geq 60 \text{ mL/min/1.73 m}^2$  for participants with creatinine levels above  $1.5\text{x}$  ULN
  - coagulation profile INR  $\leq 1.5\text{x}$  ULN unless the participant is receiving an anticoagulant
  - triglyceride level  $< 500 \text{ mg/dL}$  or  $< 5.7 \text{ mmol/L}$
  - cholesterol level  $< 400 \text{ mg/dL}$  or  $< 10.34 \text{ mmol/L}$
9. Baseline tumor measurements must be documented from imaging within 28 days prior to study registration. Other non-laboratory tests must be performed within 28 days prior to study registration.
10. Female subjects of childbearing potential should have a negative urine or serum pregnancy test within 14 days of study registration. Female subjects of childbearing potential should have a negative urine or serum pregnancy test repeated within 72 hours prior to receiving the first dose of study medication. If the urine test is positive or cannot be confirmed as negative, a serum pregnancy test will be required.
11. Female and male subjects of childbearing potential must agree to use an adequate method of contraception (hormonal or barrier method of birth control; abstinence) prior to study entry, for the duration of study participation, and 4 months after completion of tretinoin administration. Contraception is required before starting the first dose of study medication through 120 days after the last dose of study medication. Note: Abstinence is acceptable if this is the usual lifestyle and preferred contraception for the subject. **There is a significant risk of fetal malformation if pregnancy occurs while on tretinoin at any dose level, even if for short exposure periods.**
12. Be willing and able to provide written informed consent for the trial.

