#### 11.1.1 Definitions

Evaluable for Target Disease response. Only those participants who have measurable disease present at baseline, have received at least one cycle of therapy, and have had their disease re-evaluated will be considered evaluable for target disease response. These participants will have their response classified according to the definitions stated below. (Note: Participants who exhibit objective disease progression prior to the end of cycle 1 will also be considered evaluable.)

Evaluable Non-Target Disease Response. Participants who have lesions present at baseline that are evaluable but do not meet the definitions of measurable disease, have received at least one cycle of therapy, and have had their disease re-evaluated will be considered evaluable for non-target disease. The response assessment is based on the presence, absence, or unequivocal progression of the lesions.

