### 11.1.2 Disease Parameters

Measurable disease. Measurable lesions are defined as those that can be accurately measured in at least one dimension (longest diameter to be recorded) as  $\geq 20$  mm by chest x-ray or  $\geq 10$  mm with CT scan, MRI, or calipers by clinical exam. All tumor measurements must be recorded in millimeters (or decimal fractions of centimeters).

Note: Tumor lesions that are situated in a previously irradiated area might or might not be considered measurable. If the investigator thinks it appropriate to include them, the conditions under which such lesions should be considered must be defined in the protocol.

Malignant lymph nodes. To be considered pathologically enlarged and measurable, a lymph node must be  $\geq 15$  mm in short axis when assessed by CT scan (CT scan slice thickness recommended to be no greater than 5 mm). At baseline and in follow-up, only the short axis will be measured and followed.

Non-measurable disease. All other lesions (or sites of disease), including small lesions (longest diameter  $< 10$  mm or pathological lymph nodes with  $\geq 10$  to  $< 15$  mm short axis), are considered non-measurable disease. Bone lesions, leptomeningeal disease, ascites, pleural/pericardial effusions, lymphangitis cutis/pulmonitis, inflammatory breast disease, abdominal masses (not followed by CT or MRI), and cystic lesions are all considered non-measurable.

Note: Cystic lesions that meet the criteria for radiographically defined simple cysts should not be considered as malignant lesions (neither measurable nor non-measurable) since they are, by definition, simple cysts.

‘Cystic lesions’ thought to represent cystic metastases can be considered as measurable lesions, if they meet the definition of measurability described above. However, if non-cystic lesions are present in the same participant, these are preferred for selection as target lesions.

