Target lesions. All measurable lesions up to a maximum of 2 lesions per organ and 5 lesions in total, representative of all involved organs, should be identified as **target lesions** and recorded and measured at baseline. Target lesions should be selected on the basis of their size (lesions with the longest diameter), be representative of all involved organs, but in addition should be those that lend themselves to reproducible repeated measurements. It may be the case that, on occasion, the largest lesion does not lend itself to reproducible measurement in which circumstance the next largest lesion which can be measured reproducibly should be selected. A sum of the diameters (longest for non-nodal lesions, short axis for nodal lesions) for all target lesions will be calculated and reported as the baseline sum diameters. If lymph nodes are to be included in the sum, then only the short axis is added into the sum. The baseline sum diameters will be used as reference to further characterize any objective tumor regression in the measurable dimension of the disease.

Non-target lesions. All other lesions (or sites of disease) including any measurable lesions

over and above the 5 target lesions should be identified as **non-target lesions** and should also be recorded at baseline. Measurements of these lesions are not required, but the presence, absence, or in rare cases unequivocal progression of each should be noted throughout follow up.

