##### 11.1.4.2 Evaluation of Non-Target Lesions

Complete Response (CR): Disappearance of all non-target lesions and normalization of tumor marker level. All lymph nodes must be non-pathological in size (<10 mm short axis).

Note: If tumor markers are initially above the upper normal limit, they must normalize for a patient to be considered in complete clinical response.

Non-CR/Non-PD: Persistence of one or more non-target lesion(s) and/or maintenance of tumor marker level above the normal limits.

Progressive Disease (PD): Appearance of one or more new lesions and/or *unequivocal progression* of existing non-target lesions. *Unequivocal progression* should not normally trump target lesion status. It must be representative of overall disease status change, not

a single lesion increase.

Although a clear progression of “non-target” lesions only is exceptional, the opinion of the treating physician should prevail in such circumstances, and the progression status should be confirmed at a later time by the review panel (or Principal Investigator).

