#### 11.1.4.4 Evaluation of Best Overall Response

The best overall response is the best response recorded from the start of the treatment until disease progression/recurrence (taking as reference for progressive disease the smallest measurements recorded since the treatment started). The patient's best response assignment will depend on the achievement of both measurement and confirmation criteria.

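### Eligibility item 2 accepts a 1 cm short-axis node as measurable while Section 11.1.2 requires 15 mm, so a patient with no target lesion can enter the ORR denominator

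*Protocol*

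**What the plan says.** Protocol 3.1 item 2 requires at least one RECIST v1.1 measurable lesion outside the CNS and supplies its own definition. The lesion must be accurately measurable in one dimension, with "longest diameter to be recorded for non-nodal lesions and short axis for nodal lesions", and at least 1 cm on CT or MR imaging. It gives no separate limit for nodes and does not refer to Section 11.

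Protocol 11.1.2 sets a different limit for nodes: "To be considered pathologically enlarged and measurable, a lymph node must be" at least 15 mm in short axis. Nodes of 10 to under 15 mm short axis are listed among the lesions that "are considered non-measurable disease". Target lesions come from "All measurable lesions up to a maximum of 2 lesions per organ and 5 lesions in total", so a node below 15 mm cannot be one. Under 11.1.1, "Only those participants who have measurable disease present at baseline" (and who meet the treatment and re-assessment conditions) are evaluable for target disease response.

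The analysis population does not use that evaluability rule. Protocol Section 13 (Analysis and Accrual Estimates) and the SAP section of the same name both define the primary efficacy population as all eligible patients who begin treatment. Protocol 1.1 states the intent that every participant has measurable disease.

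**The concern.** Two sections of one protocol give different answers to whether a node of 10 to under 15 mm is measurable. Eligibility follows the looser answer and response scoring the stricter one. Because the ORR denominator is defined by eligibility and treatment start, item 2 decides who is in it, and no later rule takes out a patient who lacks a target lesion.

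The error can go either way:

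- **Case (a):** the patient has one small node plus other non-measurable disease that persists. There is no target sum, so partial response cannot be scored, and the persisting disease blocks complete response. The patient can only lower ORR.
- **Case (b):** small nodes are the only disease. The non-target rules then apply, and shrinkage below 10 mm can be scored as complete response, even when the change is far short of the 30% needed for a partial response. The patient can raise ORR.

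With 14 and 6 patients, one classification visibly moves the reported rate. The results of the six Cohort 2 patients also feed the decision on further design changes and on continuing or closing accrual.

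**Working it through.** **1. The plan's own figures.** Inputs from Protocol Section 13 and the SAP: stop if at most 1 of 14 respond; positive if more than 4 of 25 respond; response rates 10% and 28%.

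- Early stop at 10%: 0.9^14 + 14 × 0.1 × 0.9^13 = 0.2288 + 0.3559 = 0.5846 (stated 58%).
- P(positive) = Σ over x ≥ 2 of C(14,x) p^x (1−p)^(14−x) × P(Y ≥ max(0, 5−x)), with Y binomial (11, p). This gives 0.0908 at 10% (stated 9%) and 0.8476 at 28% (stated 85%).

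The stated design figures reproduce, and aligning the nodal limit changes none of them.

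**2. The definitions side by side.**

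| Lesion | 3.1 item 2 | 11.1.2 |
|---|---|---|
| Non-nodal, longest diameter | at least 1 cm | at least 10 mm (CT or MRI) |
| Node, short axis at least 15 mm | qualifies | measurable |
| Node, short axis 10 to under 15 mm | qualifies | non-measurable |

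Only the third row conflicts. It matters only for a patient with no other measurable lesion.

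**3. What happens to such a patient.** The patient meets item 2, starts treatment and so enters the ORR population. There is no target lesion, and response is read from the table for non-measurable disease in 11.1.4.4. Complete response there needs "Disappearance of all non-target lesions and normalization of tumor marker level" (markers matter only if initially raised) and no new lesion. For nodes: "All lymph nodes must be non-pathological in size (<10 mm short axis"). In addition, "best response assignment will depend on the achievement of both measurement and confirmation criteria".

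**4. How small a change can count in case (b).** Percentage fall to 9 mm = (baseline − 9) / baseline:

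- from 10 mm: 10.0%
- from 11 mm: 18.2%
- from 12 mm: 25.0%
- from 13 mm: 30.8%

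The first three are below the 30% that a target lesion would need for partial response. Conversely, a 30% fall ends below 10 mm whenever baseline is below 10 / 0.7 = 14.29 mm. With a single node, having no partial-response category therefore costs the patient almost nothing, while the complete-response route is easier.

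**5. Size.** One response is 1/14 = 7.1 points in Cohort 1 and 1/6 = 16.7 points in Cohort 2. The documents do not give the number of affected patients or the response counts, so the counts below are assumed. Intervals are exact 95%: lower limit Beta(0.025; x, n−x+1), upper limit Beta(0.975; x+1, n−x), with the lower limit 0 when x = 0.

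| One affected patient | As the text allows | Alternative |
|---|---|---|
| (a) non-responder kept or removed, Cohort 1 | 1/14 = 7.1% (0.2 to 33.9) | 1/13 = 7.7% (0.2 to 36.0) |
| (a) non-responder kept or removed, Cohort 2 | 2/6 = 33.3% (4.3 to 77.7) | 2/5 = 40.0% (5.3 to 85.3) |
| (b) scored as complete response or not, Cohort 1 | 1/14 = 7.1% (0.2 to 33.9) | 0/14 = 0% (0 to 23.2) |
| (b) scored as complete response or not, Cohort 2 | 3/6 = 50.0% (11.8 to 88.2) | 2/6 = 33.3% (4.3 to 77.7) |

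The last row also spans the plan's illustration for Cohort 2, where the one-sided 90% lower limit is above 10% with 3 of 6 responders (20.1%) and below it with 2 of 6 (9.26%; the plan's table shows 9.2%).

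**The case against.** The best defence is that item 2 names RECIST v1.1, Section 11 adopts RECIST v1.1 and gives the full nodal rule, and 1.1 says all participants have measurable disease. On that reading item 2 is a loose summary and Section 11 governs. The intent is indeed clear. But item 2 does not stop at the label: it gives its own definition, names the nodal short axis, sets 1 cm and never points to Section 11. Someone screening by the text as written would accept a 10 mm node.

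Second, the affected group is small. Section 2.1 describes recurrences in lungs, liver and bones, and any lung or liver lesion of at least 10 mm removes the problem. Item 1 requires disease not amenable to curative surgery, which makes disease confined to small nodes (case b) less likely still. This stands: no document shows such a patient.

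Third, the consequences are limited. Cohort 1 accrual is suspended, Cohort 2 was added for safety and tolerability, and its 3-of-6 figure is not a binding rule. Case (a) in Cohort 1 moves ORR by only about 0.6 points (7.1% against 7.7%), and counting unscorable patients as non-responders is conservative. All of this stands and limits the weight of the point. It does not cover case (b), where the error favours the drug.

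The remaining safeguards are partial. Independent review under 11.1.7 is recommended, not required, and covers responses, so it would not pick up a case (a) non-responder. The allowance of 2 for ineligible patients does not help, because the patient is eligible under item 2.

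**Conclusion.** The contradiction is real and should be corrected. As written, item 2 admits a patient whose only qualifying lesion is a node of 10 to under 15 mm. Section 11 gives that patient no target lesion, and the Protocol and SAP analysis population keeps the patient in the ORR denominator.

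Confidence in the textual conflict is high; its effect on the result is unknown. If no such patient exists, nothing changes. If one does, ORR is understated in case (a) or may be overstated in case (b). A changed response classification moves it by 7.1 points in Cohort 1 or 16.7 in Cohort 2. Case (b) is a corner case: it needs small nodes as the only disease, no new lesion, normal markers if initially raised, and confirmation. No current decision rule is shown to be affected, and the two-stage operating characteristics are not in question.

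**What to change.** - Before any further patient is registered, align 3.1 item 2 with 11.1.2: a non-nodal lesion of at least 10 mm longest diameter, or a lymph node of at least 15 mm short axis. Keep item 2's restrictions to non-CNS lesions and to CT or MR imaging, and add a cross-reference to 11.1.2 so that there is only one definition.
- Check the baseline lesions of the 14 Cohort 1 patients, and of any Cohort 2 patients already entered, against 11.1.2.
- Only if someone lacks a Section 11 measurable lesion, report ORR with its exact 95% interval with and without those patients, by cohort.

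The cost is one line of eligibility text and a short review of existing baseline records. A rare patient whose only candidate lesions are small nodes would no longer qualify. Sample size and decision rules stay as they are.
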